Study Objective(s)	 Primary To determine the feasibility and acceptability of a 4-week mindfulness training program adapted from MBSR for adults with CNCP recruited from UNC pain management clinics Secondary To test the preliminary effects of the mindfulness training program on pain-related, quality of life (QOL), and psychological outcomes. 						
Test Article(s) (If Applicable)	The intervention is based on MBSR, an 8-week mindfulness training program developed to help people manage stress-related and chronic conditions. The adapted mindfulness intervention will consist of four, weekly 1 hour and 30 minute group sessions that are modified from the original program to fit the shorter length and to directly address chronic pain management.						
Study Design	This feasibility study uses a single-arm, mixed-methods repeated measures design, with quantitative measures administered within 1 week pre and post-intervention, and qualitative semi-structured interviews administered within one to two weeks post-intervention.						
Subject Population	Inclusion Criteria						

key criteria for Inclusion and Exclusion:	Adults aged 18 and older who are able to read and speak English					
	Diagnosed with one or more CNCP conditions (daily pain at least 3 months duration) who report more than minimal pain bothersomeness and interference with activities					
	3. Has established care with provider who manages pain					
	Exclusion Criteria					
	 Diagnosis of mental illness with psychotic features 					
	History of inpatient admission for psychiatric disorder in past 2 years					
	3. Active substance abuse within the past year					
	 Completed an MBSR or other mindfulness course; has had a regular mindfulness practice during the course of the chronic pain condition 					
Number Of Subjects	24					
Study Duration	Each subject's participation will last up to 12 weeks including possible wait-time between screening and intervention start.					
	The entire study is expected to last up to 12 months.					
Study Phases Screening Study Treatment Follow-Up	(1) Screening : Phone screening with study personnel to determine eligibility for study. If eligible, the consent form will be reviewed with the participant over the phone and online written consent will be obtained after the phone call and before completing baseline measures.					
	(2) Baseline Measures: Administered via online self-report questionnaires					
	(3) Intervention : Four weekly, 1 hour 30 minute group mindfulness training sessions co-facilitated by an experienced mindfulness instructor (Faculty advisor [name]) and a clinical psychologist with pain psychology training (PI [name]).					
	(4) Post-measures: Within 1-2 weeks after intervention, administered via online self-report questionnaires and with semistructured phone interview.					
Efficacy Evaluations	Feasibility and acceptability will be measured with 1) enrollment statistics, 2) study retention, 3) assessment completion, 4) session attendance, 4) home practice diaries, and 5) credibility questionnaire and semi-structured phone interviews assessing participant satisfaction. Secondary outcomes will be measured with self-report questionnaires.					

Pharmacokinetic Evaluations	N/A
Safety Evaluations	Participant self-report of adverse experiences in response to mindfulness meditation practice. Will assess during intervention sessions. Will monitor AEs/SAEs that may or may not be study related as reported by participants.
Statistical And Analytic Plan	Primary feasibility/acceptability outcomes will be analyzed using percentages and 95% CIs. The qualitative description method will be used for interview data by identifying major themes within the content and producing a descriptive summary of the data. Secondary outcomes will be analyzed using paired t-tests and by examining the pre/post intervention change in scores and their respective standard errors with 95% confidence intervals.
Data And Safety Monitoring Plan	The PI ([name]) is responsible for data quality management and ongoing assessment of participant safety. The faculty advisor ([name]) will advise PI [name] on issues of data quality management and assessment of safety.

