3.1 Study Design

This is a single-arm, mixed-methods, repeated-measures study of a 4-week mindfulness training program for adults being treated for CNCP within UNC pain management clinics.

Screening: Potential participants will hear about this study through their pain management providers (physician/PA/nurse/clinical pharmacist/mental health) or flyer advertisements, and interested patients will contact study personnel for complete a phone screening interview. If a participant is deemed eligible, the PI/research assistant will review the information in the consent form with the participant over the phone and answer any questions. Participants will provide written consent online via a REDCap survey link.

Baseline: Baseline measures will be completed by participants within the week prior to starting the intervention. Participants will receive an email with a link to a REDCap survey containing the self-reported questionnaires. Questionnaires should take approximately 30 minutes to complete. Intervention: The intervention will consist of four weekly, 1 hour and 30 minute group mindfulness training sessions. It will take place at a UNC clinic or conference room location. The intervention will be adapted from the standard 8-week MBSR program to fit the shorter class duration and to pertain specifically to chronic pain management. Mindfulness skills will include sitting meditation with attention to breathing, body scan meditation, mindfulness of daily routine activities, and expanding practice to notice and release fixation on thoughts, emotions, or sensations. Participants will be given guided audio recordings of mindfulness practices and course handouts and asked to complete home practice assignments daily during the course. They will also be sent a brief REDCap survey daily to record their daily home practice of mindfulness skills and daily pain intensity. Follow up: Post-intervention measures will be completed by participants via an online REDCap survey within one to two weeks after the final intervention session. Also within one to two weeks of the final intervention session, participants will be scheduled to complete a 20 to 30 minute semi-structured phone interview assessing their experience (satisfaction, challenges, suggestions for improvement) with the intervention.

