4.3 Intervention procedures (by visits)

The mindfulness intervention will consist of four, weekly group mindfulness skills sessions each lasting 1 hour and 30 minutes. Each session will allow time for a 5-minute break in the middle. Sessions will be co-instructed by PI [name] and faculty advisor [name]. All sessions will take place at the same location. See **Appendix B** for session-by-session content and home practice assignments. Participants will receive guided audio recordings for mindfulness skills practice, in addition to a binder with course handouts. The instructor will send one email to each participant the day after each session summarizing the session content and home practice assignments and encouraging participants to complete the daily mindfulness practice diaries. Sessions will be recorded to monitor fidelity to the intervention protocol. Participants will be asked to complete daily home practice and pain intensity diaries between session weeks 1 and 4 via online REDCap surveys that will be sent by email on a daily basis.

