4.4 Follow- up procedures (by visits)

Post-Test Questionnaires: After the final intervention session (week 4), participants will be emailed a link with a REDCap survey containing all of the questionnaires from the

baseline survey, excluding demographic information. It will also include questions on intervention credibility.

Post-Test Interview: With-in 1 to 2 weeks after the final session, participants will be scheduled for a 15 to 30-minute semi-structured phone interview with the PI to assess participants' experience with the intervention sessions and overall study. Questions will address the following: satisfaction and usefulness of the skills and content, acceptability of the format, any challenges, and any suggestions for improvement of the intervention or study procedures.

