4.8 Subject Completion/ Withdrawal procedures

Subject Completion: Participants' enrollment in the study will be considered complete once the intervention sessions have ended, post-test measures and phone interview are complete, and study compensation provided. Should participants not complete the post-test survey or phone interview, their participation will be complete when the window to complete such assessments has passed and they have been compensated for any completed study procedures.

Subject Withdrawal: Should a participant choose to withdraw from the study for any reason, their withdrawal will be documented in the case report form (**see Appendix D**) and they will be provided with any study compensation that may still be pending based on completed study procedures. Should any adverse event occur during study enrollment that prohibits a participant from completing study procedures, the participant will be withdrawn from the study and provided with any study compensation that may still be pending based on completed study procedures.

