Appendix B. Measures

Scale or Item	Description
Screening Measures/Items	
Drug Abuse Screening Test ²⁷ (DAST)-10	10 items; assess drug use in the past 12 months
Alcohol Use Disorders Identification Test	3 items; assesses alcohol consumption, drinking
(AUDIT) ^{28,29}	behaviors, and alcohol-related problems
Chronic pain	Have you experienced pain on a daily basis for at least
	3 months?
Pain bothersomeness	How bothersome was your pain in the previous week?
	(rating scale 0-10).
Pain interference with general activities	How much did your pain interfere with your general
	activities in the past week? (rating scale 0-10).
Diagnosis of mental illness with psychotic	Have you ever been diagnosed with schizophrenia,
features	schizoaffective disorder, or another psychiatric
	disorder with psychotic symptoms?
Psychiatric hospitalization in past 2 years	Have you ever been hospitalized for mental health
	reasons? When was the last hospitalization?
Previous mindfulness training	Have you ever participated in mindfulness training or
	course? Have you ever had a regular mindfulness
	practice? When?
Baseline-only Measures	
Demographic variables	Age, race/ethnicity, education, income, marital status
Pain conditions and regions	e.g. fibromyalgia, osteoarthritis, low-back pain,
	migraine, neck pain, etc
Baseline and Post-test Measures*	
Pain Medication Use	Pain medications taking, frequency, and dose
Physical Function (short-form 4a) ³⁰	4 items; difficulty with activities of daily living
Anxiety (sf 4a)	4 items; suggestive of anxiety in the past 7 days
Depression (sf 4a)	4 items; suggestive of depressed mood in past 7 days
Sleep Disturbance (sf 4a)	4 items; sleep quality and disturbance in past 7 days
Pain Interference (sf 6b)	6 items; degree to which pain interferes with life
Pain Intensity	1 item; average pain intensity past 7 days (0-10)
Positive Affect and Wellbeing	9 items;
Perceived Stress Scale – 4	4 items; global measure of perceived stress
Pain Catastrophizing Scale ³¹	13 items; 3 subscales characterizing thoughts and
	feelings when in pain – rumination, magnification,
	helplessness
Chronic Pain Acceptance Questionnaire ³²	20 items; acceptance of experiencing pain
Freiberg Mindfulness Inventory	14 items; measures all aspects of mindfulness
Intervention Satisfaction	1 likert-type item asking how satisfied are with the
2.22	intervention oveall
Credibility Questionnaire ^{34,35} (after session	5 items assessing opinions about the intervention

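### Does the one-week versus two-week wording for the post-test survey leave the completion counts or the pre/post changes undefined?

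*Combined protocol and SAP*

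**What the plan says.** Four places in the combined protocol and SAP bear on when the post-test survey is due.

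- Synopsis, Study Design row: "with quantitative measures administered within 1 week pre and post-intervention, and qualitative semi-structured interviews administered within one to two weeks post-intervention". Survey and interview have separate windows, and the survey's upper limit is one week.
- Synopsis, Study Phases row: "Within 1-2 weeks after intervention, administered via online self-report questionnaires", with the interview in the same entry. The upper limit is two weeks.
- Section 3.1: "Post-intervention measures will be completed by participants via an online REDCap survey within one to two weeks after the final intervention session". The upper limit is two weeks.
- Section 4.4: "After the final intervention session (week 4), participants will be emailed a link with a REDCap survey". No closing date is given for the survey; the one-to-two-week period there applies to the interview.

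Two other parts of the plan touch the window. Section 4.8 treats enrolment as complete once "post-test measures and phone interview are complete", sessions have ended and compensation is paid. For a participant who does not return the survey or do the interview, it closes participation when the assessment window has passed, without giving its length. Section 6.1 lists retention (goal 85%) and the proportion of completed assessments (no numeric goal) among the feasibility outcomes.

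Appendix B states a past-week recall for four outcomes: depression, sleep disturbance, pain intensity and anxiety (the last described as "4 items; suggestive of anxiety in the past 7 days").

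**The concern.** In a feasibility study, the rule for what counts as a completed assessment is part of the primary outcome. A survey returned on days 8-14 is in time under section 3.1 and late under the Study Design row. If section 4.8 is read as shutting out late returns, two teams following different lines of the plan could report different completion and retention percentages from the same data.

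The window also affects what the 7-day-recall scores describe. According to section 4.3, "Participants will be asked to complete daily home practice and pain intensity diaries between session weeks 1 and 4". A survey answered soon after session 4 therefore looks back largely into the last week of the course, and one answered in the second week looks back only at time after it. Section 6.3 has no timing rule for the paired comparisons, and section 6.4 intends the data for planning a larger trial, where the time point of the effect should be known.

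**Working it through.** **1. Do the places conflict?** Yes. Both synopsis rows speak of the survey being administered, so the difference is not one of sending against completing. Counting week 1 as part of one to two weeks does not remove it either, because the upper limits are still day 7 and day 14. Section 4.4 is silent on a survey deadline and so does not conflict. Because it sends the link after the last session with no stated delay, it favours reading the longer window as any time up to day 14 over days 7-14 only.

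**2. Does any planned figure use the window?** The section 6.4 figures were recomputed.

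- Retention half-width: 1.96 × √(0.85 × 0.15 / 24) = 0.143, interval 0.707 to 0.993 (stated 0.14; 0.71, 0.99).
- Attendance, with design effect 1 + (4 − 1) × 0.10 = 1.3: 1.96 × √(1.3 × 0.75 × 0.25 / 96) = 0.099, interval 0.651 to 0.849 (stated 0.10; 0.65, 0.85).
- Number at post-test: 24 × 0.85 = 20.4 (stated 20).

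All reproduce, and none has the survey window as an input.

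**3. Does the window change a count?** Only if a returned survey is thrown out for being late. Each exclusion would lower a proportion of the 24 enrolled by 1/24 = 4.2 points. Section 4.8 does not order this. It says when participation ends for someone who has not completed an assessment, and it links that to compensation. It also refers to one window for survey and interview together. The interview is given up to two weeks in both synopsis rows, in 3.1 and in 4.4. On that reading the 4.8 window does not close before day 14, even under the Study Design row, and a survey returned on days 8-14 arrives before closure.

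**4. What happens to the 7-day recall?** For a survey answered d days after session 4, the share of the recall period before that session is max(0, (7 − d)/7).

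| Day of survey | Share before session 4 |
|---|---|
| 0 | 7/7 = 100% |
| 1 | 6/7 = 86% |
| 3 | 4/7 = 57% |
| 7 or later | 0% |

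If replies are spread evenly (an assumption; the documents give no return pattern), the average share is 50% over days 0-7, and (7 × 50% + 7 × 0%)/14 = 25% over days 0-14. The shorter window already spans the whole range from 100% to 0%. Choosing it would reduce the mixture of periods but not remove it.

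**5. How many outcomes are involved?** Four have a stated 7-day recall. Appendix B states none for physical function, pain interference, positive affect, perceived stress, catastrophizing, acceptance or mindfulness.

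**The case for a change.** The best case for a change is that a feasibility study should leave no doubt about what counts as complete, and that no section says the body text overrides the synopsis. Suppose, for illustration, that 21 of 24 surveys are in by day 14. If one came after day 7 and was excluded, the figure would fall from 21/24 = 87.5% (exact 95% CI 67.6-97.3%) to 20/24 = 83.3% (62.6-95.3%), crossing 85% if retention were counted by survey return. With three late it would be 18/24 = 75.0% (53.3-90.2%).

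The arithmetic is right, but it needs the synopsis phrase to prevail over section 3.1 and late surveys to be discarded. The plan says neither. The late counts are assumed, the intervals overlap widely, and no decision rule hangs on the 85% goal.

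The recall argument stands in a narrower form: the longer window admits surveys whose 7-day recall falls wholly after the course. The documents do not show how scores move after session 4, so no effect on scores can be stated. Sections 5.1 and 6 also say the study is not powered for efficacy or for changes in secondary outcomes.

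It is also true that section 6.1 does not define retention in full, and that the status form does not say how to code a participant with no post-test data. Those are separate matters that settling the survey window would not resolve.

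**Conclusion.** The plan contains a clerical inconsistency: one synopsis phrase has a one-week survey limit where another synopsis row and section 3.1 have two weeks. No change to the plan follows. Following section 3.1 and counting every survey returned gives sound feasibility percentages and valid paired changes; so would the shorter window. No stated figure, threshold or planned analysis depends on which is used.

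The possible size is 4.2 points per excluded survey, and nothing calls for exclusion. For four secondary measures there is a shift in recall period, from an average of 50% before session 4 to 25% under even return, with unknown effect on scores. An analyst who wants to describe timing can do so already: the Subject Status form in Appendix C has a date for the post-intervention assessment, and each group shares its session dates.

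This conclusion rests on reading section 4.8 as administrative closure and the longer window as any time up to day 14. If the investigators did exclude surveys from days 8-14, the completion figures could move as shown above, but that would be a step the plan does not contain.

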1 BACKGROUND AND RATIONALE

1.1 Introduction

Chronic pain is a costly and debilitating condition affecting over 100 million U.S. adults.¹ Over 10% of North Carolinians are affected by chronic low back pain alone.² Chronic non-cancer pain (CNCP) is commonly treated with pharmacotherapy, with 3-4% of the entire U.S. population prescribed long-term opioid therapy.³ Remarkably, the effectiveness of long-term opioid use for CNCP has limited evidence^{4,5}; furthermore, chronic opioid use can lead to increased pain sensitivity⁶ and increased risk for opioid use disorders and overdose.^{7,8} Thus, the nonpharmacologic management of CNCP is strongly recommended by the Centers for Disease Control and was named a top scientific priority of the NIH-National Center for Complementary and Integrative Health.⁹

CNCP is associated with disability, decreased quality of life (QOL) and emotional distress. ¹⁰ Mindfulness Based Stress Reduction (MBSR) is an established mind-body intervention shown to improve QOL, functioning and depression across pain conditions. ¹¹ It has led to clinical improvements (>30%) in functional disability in 61% of low back pain patients, similar to cognitive behavioral therapy and more effective than usual care. ¹² Mindfulness training targets changing one's reaction to painful experiences with nonjudgmental, present-moment awareness¹³, and improves the self-management of pain through increased self-regulation of emotions and attention. ¹⁴ Mindfulness training has decreased opioid use disorders and cravings. ¹⁵ However, the time demand of standard MBSR (26 class hours in 8 weeks) is a key barrier for those whose condition or circumstances limit ability to participate. ^{16,17} Brief mindfulness training programs based on MBSR have been piloted for specific chronic pain conditions such as tension-type headache¹⁸ and low back pain¹⁹, but have not been studied in groups with CNCP of varied etiologies in a clinical setting.

1.2 Name and Description of Investigational Product or Intervention

The current study will use an adapted version of the established mindfulness training program called Mindfulness-based Stress Reduction (MBSR). MBSR is the most popular and well-tested format for teaching mindfulness skills in the U.S. MBSR was developed by [name] to teach a range of mindfulness skills to help individuals better manage chronic and stress-aggravated illnesses.^{20,21} Mindfulness skills involve the intentional self-regulation of attention to present-moment experience, combined with releasing cognitive fixation on thoughts and emotions regarding the past or future.¹³ The MBSR program teaches a range of mindfulness-related skills, typically in an eight-week, 2.5 hour per week group format, with a 6-hour weekend day of mindfulness retreat. It is generally available to medical patients and community members with a wide range of stress-related problems or medical conditions. The current study will use an adapted version of this program, adapted by PI [name] and Faculty Advisor [name]. It will be adapted to fit the shorter length (4 weeks; 1 hour, 30 minute sessions) and will be directly related to chronic pain management and coping. See **Appendix B** for a breakdown of sessions content and mindfulness skills taught.

1.3 Non-Clinical and Clinical Study Findings

Potential benefits: Studies indicate that mindfulness-based interventions such as MBSR may have a number of pain-related and psychological benefits for individuals with chronic pain of mixed etiologies. In studies of CNCP, mindfulness intervention have been shown to reduce depression^{22,23}, anxiety, perceived stress, and pain perception²³ and improve quality of life²², physical functioning¹², and pain acceptance.²⁴

Potential risks: Based on results of previous literature, we expect there to be no more than minimal risk in this study; however, literature on MBSR has not systematically included adverse event reporting, although most studies have not reported any serious risk from participating in MBSR. There have been reports of increased emotional distress and increased awareness of both positive and negative experiences, which may initially increase distress when participants are not used to directing attention towards unpleasant thoughts, feelings, and sensations. ²⁵ The MBSR curriculum guide by [name] notes the potential for increased negative emotions at the beginning of the course, as well as the possibility that history of trauma, abuse, recent loss, or substance addiction could heighten negative emotional reactions. With an experienced instructor, reactions can be managed and appropriate referrals made. ²⁵

